3. PLANNED ANALYSES

3.1. Final Analyses

The final planned primary analyses will be performed after the completion of the following sequential steps:

- 1. All participants have completed (or withdrawn from) the study as defined in the protocol.
- 2. All required database cleaning activities have been completed, final database was released, and database lock has been declared by Data Management.

4. ANALYSIS POPULATIONS

Population	Definition / Criteria	Analyses Evaluated
Safety analysis	• All randomised subjects who received at	• Safety
set	least one dose of HB-adMSCs infusion or	 Study Population
	one dose of placebo.	
	• If participants receive a treatment different	
	to their randomized treatment, they will be	
	analysed according to the treatment that	
	was actually received.	
Efficacy	All randomized participants who received	• Efficacy
analysis set	all 6 infusions of either HB-adMSCs or	
	placebo.	
	• Participants will be analysed according to	
	their randomized treatment.	

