- 4. Principal Investigator may stop the infusion at any time, based upon PI's discretion.
- 5. Malignant Hypertension (180/120 mm/Hg)

Confidential

6. Sudden Severe Hypotension (30-40 mm/Hg drop from pre-infusion level)

If an infusion is stopped for a subject due to an adverse event or serious adverse event, including but not limited to hypersensitivity reaction/anaphylaxis, no additional study treatment will be given to the study participant who develops the event. Although, the study participant will not receive the investigational product, he or she must be followed for safety purposes according to the protocol.

Study Stopping Rules

This Clinical Trial will stop if any of the following events are present:

- 1. Subject's Death.
- 2. Occurrence of any thromboembolic event during or after HB-adMSCs administrations (up to 72 hours).
- 3. Any cerebrovascular ischemia or seizure event occurring within 72 hours after any of the investigational product administrations.
- 4. Any Serious Adverse Events determined to be related to the following:
 - When there is one CTCAE.v5 grade 4 or 5 AE, irrespective of attribution.
 - Either any CTCAE Grade 2 adverse event that persists for more than two weeks, or any Grade 3 adverse event, that occurs within 72 hours after product administration.

Should the study participant discontinue study treatment he/she will be followed for safety according to the protocol safety monitoring plan. The study participant will receive follow up communication to ascertain the outcome until resolved fully. All will be documented as per protocol.

Statistical Methods

Sample size consists of up to 24 subjects who have been diagnosed with Parkinson's disease. All data collected from subjects who are enrolled and received the investigational product will be analyzed. The incidence of Adverse Events and Serious Adverse Events will be recorded and reported. Efficacy will be measured by improvement of subject's signs and symptoms associated with Parkinson's disease. Interim analysis of all safety and efficacy data may be performed at any time deemed appropriate by the Sponsor. Although, the subject's data may be analyzed at any time, a data analysis of all available data will be conducted when a least 10 subjects in each group have completed Week 24. Data may be analyzed for internal informational purposes, reports, presentations, and manuscripts.

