2.2. Study Design

Overview of	Study Design and Key Features
Randomized,	double-blind, placebo-controlled, parallel group study
Design Features	 Randomized, double-blind, Placebo controlled, parallel group study. 24 Subjects 2 Treatment groups Group 1 → HB-adMSCs Group 2 → Placebo Duration of treatment: up to 32 weeks. The overall study includes screening (up to 4 weeks prior to randomisation), 6 treatment visits after randomisation scheduled according to the following schedule: Infusion 1 (Week 0), Infusion 2 (Week 4), Infusion 3 (Week 8), Infusion 4 (Week 16), Infusion 5 (Week 24) and Infusion 6 (Week 32). After all the treatments were administered to the patients, there will be two follow up visits, the first one the Week of 42, and the second one, at the end of study, at Week 52.
Dosing	 HB-adMSCs (Hope Biosciences adipose derived mesenchymal stem cells) will be administered as an IV infusion with the dose of 200 million cells Placebo is to be administered as an IV infusion which contains saline solution (0.9%)
Treatment Assignment	Participants will be randomised in 1:1 ratio, to receive either HB-adMSCs active treatment or Placebo.

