5.5 Interim analysis

Interim analysis of primary and secondary efficacy data will be performed. Details of the planned displays for interim are provided in **Error! Reference source not found.** Interim analysis will be conducted when at least 10 subjects from each group have completed Week 24.

For the interim analysis, subject-level data will be unblinded. The unblinded analysis of the interim outputs will be done by unblinded independent statistics and programming team, who have access to interim analysis data. An unblinded statistician, not otherwise associated with the project, will perform the interim analysis, which will include the displays shown in the **Error! Reference source not found.**, with delivery priory labelled as "INTER".

These results will be limited to the members of SPONSOR engaged in the discussion of interim analysis results, and will not be shared with the investigators.

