5.6 General Considerations

Unless otherwise stated, all hypotheses will be tested at 0.95% confidence interval (p = 0.05, two-sided test, when applicable). In other words, statistical test will look for the difference (either better results or worse results), rather than focusing solely on efficacy. All continuous measurements will be summarised descriptively at each visit, followed by treatment, using observed data.

Summary of continuous variables will be presented using the total number of participants (N), Mean, Standard Error of mean (SE), Standard Deviation (SD), Median and Range (Minimum and Maximum). The categorical variables will be presented using the number and the percentage of subjects who have provided the defined categorical answer.

For measurements obtained during course of time, mean values will be plotted to explore the trends. Observed data will be used as the basis for plotting data along with standard error (SE) or Standard Deviation (SD) represented as bars, if not otherwise specified.

A non-parametric Mann-Whitney U Test (or Wilcoxon Rank-Sum Test) will be applied on primary and secondary efficacy endpoints to test the significance of the effects of the treatment by comparing median values.

For measurements performed over time, median values will be plotted to explore the trends. Observed data will be used as the basis for plotting the data along with Inter Quartile Range (IQR) used as bars, if not otherwise specified.

A parametric, repeated measurements ANOVA will be applied as a sensitive analysis to test the significance of the effects of the treatment.

Change from baseline safety Lab measurements will be analyzed using a repeated measurements ANOVA to test the significance of the effects of the treatment.

Presentation of results from a statistical analysis model will include the estimated means caused by treatment effects, using Adjusted Mean. HB-adMSCs 200MM vs Placebo group will be compared.

For all endpoints analyzed statistically, estimated mean treatment differences will be presented together with two-sided 95% confidence intervals and p-values.

All safety evaluations will be presented using Safety analysis set while the efficacy analysis

Individual safety and efficacy parameters will be listed.

will be presented using Efficacy analysis set.

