6. STUDY POPULATION ANALYSES

6.1. Overview of Planned Study Population Analyses

The study population analyses will be based on the Safety analysis set.

Study population analyses includes analyses of subject disposition, demographic, as well as characteristics compared to baseline, including medical history, prior and concomitant medications.

Details of the planned displays are presented in Error! Reference source not found..

Categorical variables will be summarized by the number and percentage of subjects who provided a specific answer, and the continuous parameters will be summarized by N, mean, standard error of mean, median, sample standard deviation, minimum and maximum, unless otherwise specified.

Disposition summary includes subject screened and randomized, while the disposition at end of study, Week 52, along with reasons for withdrawals will be presented based on number of subjects and percentage. Subjects in different analysis sets also will be presented.

The reasons for screening failure will be presented based on number of subjects and percentage. The percentage will be calculated based on the total number of screened subjects.

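### The only efficacy set requires all six infusions, so the primary comparison depends on events after randomization and no planned efficacy analysis restores those excluded

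*SAP*

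**What the plan says.** SAP section 4 defines two sets. The Safety analysis set needs one dose and serves the safety and study-population displays. The Efficacy analysis set needs receipt of "all 6 infusions of either HB-adMSCs or" placebo, with participants kept in their randomized arm. SAP 2.2 gives the later part of the schedule as "Infusion 5 (Week 24) and Infusion 6 (Week 32", so membership is settled about 32 weeks after the first infusion.

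The Efficacy set governs every efficacy analysis in the SAP text available:

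- the general rule in 5.6, in a sentence that opens "All safety evaluations will be presented using Safety analysis set while the efficacy analysis" and goes on to name that set;
- the primary analysis (7.1.3) and the secondary analyses (7.2.3);
- both sensitivity analyses (7.1.4.1 and 7.2.4.1).

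Sections 7.1.3 and 7.2.3 allow for another population to be specified, but none is. Section 10.1.2.1 rules out imputation and excludes participants with missing data.

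On reporting, SAP 6.1 says "Subjects in different analysis sets also will be presented" and SAP 5.6 says "Individual safety and efficacy parameters will be listed". On the interim, SAP 5.5 says "Interim analysis will be conducted when at least 10 subjects from each group have completed Week 24" and names no analysis set.

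The protocol's Statistical Methods section says "All data collected from subjects who are enrolled and received the investigational product will be analyzed". Under its Infusion Stopping Rules, once an infusion is stopped for an adverse event, "no additional study treatment will be given to the study participant who develops the event", although safety follow-up continues.

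**The concern.** Randomization makes the two arms comparable at the start. A set defined by completing six infusions compares those who remain after up to 32 weeks of events that treatment may influence, such as an infusion stopped for an adverse event or one declined by the participant. Keeping participants in their randomized arm preserves the labels but brings nobody back.

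If the people removed would have done worse and more of them come from one arm, the primary test credits treatment with a difference produced by selection. With 12 per arm, two or three removals are a large share of an arm. The planned sensitivity analysis cannot reveal this, because it changes the model and keeps the set.

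The definition also does not fit the interim analysis. That analysis is triggered at Week 24, the visit of infusion 5. Read literally, a participant between Week 24 and infusion 6 is not yet in the only set assigned to efficacy.

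**Working it through.** **Text check.** Can a participant leave the efficacy set and still have a primary outcome? Yes, though it is not assured. The Infusion Stopping Rules end dosing but continue safety follow-up, and Table 3 of the protocol schedules the Parkinson's assessments at every visit through Week 52. Participants who leave the trial altogether are offered only a safety visit about 30 days after infusion (Withdrawal Criteria). So some excluded participants may have a Week 52 score and others will not.

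**Inputs from the documents.** 24 participants, 12 per arm (protocol, randomization section); Mann-Whitney test (SAP 7.1.4.1); two-sided 5% (SAP 2.3). The documents give no loss rate, SD or effect size, so there is no planned figure to reproduce.

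**Assumptions.** No true effect; normally distributed Week 52 changes y with SD 1, higher meaning worse; exact Mann-Whitney critical values for the numbers that remain. Exclusion follows a score z = ρy + √(1 − ρ²)e, with e independent standard normal, and the k highest z in the active arm are removed. There were 200,000 replicates per cell (Monte Carlo error at most about 0.08 percentage points).

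**Chance of any exclusion.** If each participant has an assumed 5% or 10% chance of missing an infusion, the chance of at least one exclusion is 1 − 0.95²⁴ = 71% or 1 − 0.90²⁴ = 92%.

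**Precision only (ρ = 0).** The SE ratio is √[(1/(12 − k) + 1/12)/(2/12)] = 1.022, 1.049 and 1.080 for k = 1, 2, 3. There is no bias.

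**Bias, analytic.** The three largest expected normal order statistics of 12 are 1.629, 1.116 and 0.793. The shift is ρ × (sum of the k largest)/(12 − k):

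- k = 1: ρ × 1.629/11 = 0.148ρ
- k = 2: ρ × 2.745/10 = 0.274ρ
- k = 3: ρ × 3.538/9 = 0.393ρ

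**Bias and total rejection rate, loss from the active arm only.** The exact size with nobody lost is 4.49%. It changes with k because the test is discrete, so each column has its own reference.

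| | k = 1 | k = 2 | k = 3 |
|---|---|---|---|
| Exact size without selection | 4.39% | 4.26% | 4.91% |
| ρ = 0.3 | 0.04 SD, 4.53% | 0.08 SD, 4.62% | 0.12 SD, 5.75% |
| ρ = 0.5 | 0.07 SD, 4.80% | 0.14 SD, 5.42% | 0.20 SD, 7.22% |
| ρ = 1 (bound) | 0.15 SD, 6.28% | 0.27 SD, 9.69% | 0.39 SD, 16.03% |

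At ρ = 0.5 the excess due to selection is 4.80 − 4.39 = 0.41, 5.42 − 4.26 = 1.16 and 7.22 − 4.91 = 2.31 percentage points. The excess is one-directional: with k = 3 and ρ = 0.5, rejections favouring active are about 6.2%, against about 2.3% with nobody excluded. For scale, the SE of the difference at 12 per arm is √(2/12) = 0.41 SD, so 0.14 SD is about a third of it.

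**Loss in both arms, ρ = 0.5 (active/placebo).** 2/1: 0.06 SD, 4.99%. 2/2: 0 SD, 4.86%. 3/1: 0.12 SD, 5.92%.

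**What a wider set removes.** Three active participants are excluded, and j of them, chosen at random, have a Week 52 score and re-enter (separate runs, so the second decimal can differ from the table above).

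| | j = 0 | j = 1 | j = 2 | j = 3 |
|---|---|---|---|---|
| ρ = 0.5 | 0.20 SD, 7.18% | 0.12 SD, 5.02% | 0.05 SD, 4.57% | 0 SD, 4.49% |
| ρ = 1 | 0.39 SD, 15.94% | 0.24 SD, 7.99% | 0.11 SD, 5.18% | 0 SD, 4.49% |

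**The case against.** The strongest reply is that the harm is hypothetical. Nothing in the documents links stopping infusions to Part II change. Exclusion is settled by about Week 32 and the outcome is measured at Week 52, so a correlation of 1 is a mathematical bound and not a realistic case. At correlation 0.5 the error rate passes about 6% only when loss is one-sided. Some severe reactions might trigger the study stopping rules and so would not accumulate as exclusions. All of this stands. It limits the size, but it does not make the definition sound.

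Set counts, withdrawal reasons and listings are planned, so an imbalance would be largely visible. That is true, but they show who is missing and not how the comparison changes. The outlier rule in SAP 10.1.2 rests conclusions on the full sets, but those are the sets already defined. The protocol sentence on analysing all dosed participants names no efficacy set, so it fits poorly with the SAP without flatly contradicting it.

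Four caveats also stand:

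- The statement that no comparison restores participants covers the available text; the planned-display lists sit behind cross-references that do not resolve.
- The figures use the 5% level of SAP 2.3. SAP 5.4 places the same endpoint in an eight-test Holm family starting at 2.5/8 = 0.3125%. At that level, three active losses with correlation 0.5 give about 0.49% against 0.24%: a similar relative rise, but small in absolute terms.
- The SAP does not say whether a partly delivered infusion counts as received.
- Changing the primary set after the sponsor has seen unblinded interim results could itself look data-driven.

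**Conclusion.** The concern holds. The text is clear: there is one efficacy set, it requires six infusions, every planned efficacy analysis uses it, and none shows the result with the excluded participants restored. The interim mismatch follows from the same definition and does not depend on how many participants drop out.

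The size of any bias is unknown and may be zero. Under the stated assumptions, one-sided loss of one to three participants with moderate outcome dependence (correlation 0.3 to 0.5) shifts the difference by 0.04 to 0.20 SD and raises type I error by at most about 2.3 percentage points. Balanced loss at correlation 0.5 gives essentially no bias. This should be fixed because the fix is cheap, not because a large distortion has been shown.

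**What to change.** In the SAP:

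- **Section 4:** define the primary Efficacy set as all randomized participants with at least one infusion, analysed as randomized. Keep the Mann-Whitney test and include every available Week 52 score, including those obtained after infusions stop. Retain the six-infusion set as a labelled per-protocol supportive analysis, and say whether a partial infusion counts towards it.
- **Sections 7.1 and 7.2:** run the efficacy and sensitivity analyses on the redefined set.
- **Section 5.5:** state that the interim uses it too.
- **Section 10.1.2.1:** state that exclusion for missing data is per analysis. For the primary test, only participants lacking a baseline or Week 52 score drop out.
- **Section 6.1:** present set counts by arm with reasons, adding participants randomized but never dosed and those who stop infusions without withdrawing.

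Make the change before anyone involved sees unblinded interim results. If that has already happened, record the timing and report both sets side by side.

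The cost is wording in these sections plus one extra run. Partly treated participants may dilute the estimate. The new set still conditions on a first infusion and an available Week 52 score, so the conditioning is milder but not absent. The gain in the primary test is limited to participants who stop infusions but have that score.

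Separately, plan to obtain Week 52 MDS-UPDRS scores from participants who leave early. This may need a protocol amendment with FDA and IRB agreement.

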5. CONSIDERATIONS FOR DATA ANALYSES AND DATA HANDLING CONVENTIONS

5.1 Study Treatment & Sub-group Display Descriptors

Treatment Group Descriptions		
Protocol treatment arm Data Displays for Reporting		
Treatment Arm	Treatment Arm	Order in TLF
Arm 1	HB-adMSCs 200MM	1
Arm 2	Placebo	2

Treatment comparisons will be displayed as follows using the descriptors as specified in the statistical analysis:

HB-adMSCs 200MM vs. Placebo

5.2 Baseline Definitions

For all endpoints, the baseline value will be the value obtained at the latest pre-treatment assessment visit (a non-missing value), including those from unscheduled visits. For example, if an assessment has been made both at screening visit (Visit 1) and infusion 1 visit (listed as Visit 2, Week 0), the value from the later, "infusion 1 visit" is used as the baseline value, if the value is collected prior to the admission of infusion. If the value measured at the Week 0 visit is missing or if it was collected on/after the dose and the assessment has been made at screening/unscheduled visits (which is prior to Week 0 visit), then the screening/unscheduled visits value is used as the baseline value.

Unless otherwise stated, if baseline data is missing, no derivation will be performed, and baseline will be set to missing.

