- Visit 1 Screening, during this visit, the principal investigator will make the decision to determine whether the screened participant is eligible and whether the next visit can be scheduled. Once, the principal investigator has evaluated the eligibility of the subject screened (up to 28 days), a randomization process will be conducted in order to assign the eligible subject either HB-adMSCs or placebo. Randomization will only apply to eligible subjects. If a study participant does not meet the inclusion and exclusion criteria during the screening process, he/she will be considered Screen Failure (SF) and does not need to be randomized to any group.
- Visit 2 Infusion 1, (**Baseline**): this visit will be used as a starting point for comparison of participant's data. During this visit, eligible study participants will receive his/her first investigational product administration or placebo with a rigorous monitoring of vital signs for a total of 2 hours after drug exposure. Other study evaluations will be completed as part of this visit.
- Visit 3 Infusion 2: approximately 4 weeks after the initial investigational product administration this visit should be completed. Other study evaluations will be completed as part of this visit.
- Visit 4 Infusion 3: approximately 8 weeks after the initial investigational product administration this visit should be completed. Other study evaluations will be completed as part of this visit.
- Visit 5 Infusion 4: approximately 16 weeks after the initial investigational product administration this visit should be completed. Other study evaluations will be completed as part of this visit.
- Visit 6 Infusion 5: approximately 24 weeks after the initial investigational product administration this visit should be completed. Other study evaluations will be completed as part of this visit.
- Visit 7 Infusion 6: approximately 32 weeks after the initial investigational product administration this visit should be completed. Other study evaluations will be completed as part of this visit.
- Visit 8 Safety Follow Up: approximately 42 weeks after the initial investigational product administration, active study participants will complete a follow up visit at the clinic site.

• Visit 9 – End of Study, during this final visit (approximately 52 weeks after Week 0) a complete group of study assessments will be performed in order to evaluate the safety and efficacy of HB-adMSCs or Placebo administrations.

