Clinical assessments of disease activity will take place during the following visits:

- Visit 1 Screening
- Visit 2 Infusion 1 (**Baseline**)
- Visit 3 Infusion 2
- Visit 4 Infusion 3
- Visit 5 Infusion 4
- Visit 6 Infusion 5
- Visit 7 Infusion 6
- Visit 8 Safety Follow Up
- Visit 9 End of Study

Blood samples for safety assessments will be collected in as follows:

- Visit 1 Screening: after informed consent has been obtained, blood samples should be collected from a vein of the study's participant arm, these lab results will help assess the subject's eligibility.
- Visit 2 Infusion 1, (**Baseline**): safety laboratory samples should be collected from a vein of the study participant in order to set a start point of comparing with the laboratory results to obtain in the following visits. Although, laboratory samples are a requirement of this visit, in certain situations this requirement will be avoided, and the laboratory results obtained during Visit 1 Screening will be used as a Baseline. See some of these situations below:
 - Period of time between Visit 1 Screening and Visit 2 Infusion 1 (Baseline) is less than 10 days.
 - The study participant had no change in medical history or concomitant medications since Visit 1 Screening.
 - No changes in physical examination are identified by principal investigator during Visit 2 – Infusion 1, (Baseline).
- Visit 6 Infusion 5: safety laboratory samples should be collected from a vein of the study's participant arm during this visit.
- Visit 9 End of Study: safety laboratory samples should be collected from a vein of the study's participant arm during this visit.

For study participants who do not complete the study trial, a safety follow-up visit will be scheduled as follows:

- For subjects who did not receive any the investigational product, a safety follow-up visit, or Early termination visit (ETV) will be scheduled as soon as possible, but not later than 30 days after the last visit.
- For subjects who received at least one dose of the investigational product, a safety follow-up visit will be scheduled approximately 30 days after that single dose.
- For subjects who received more than one dose of the investigational product, a safety follow-up visit will be scheduled after the last investigational product administration.

Withdrawal Criteria

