- 10. Study participant is unlikely to complete the study or adhere to the study procedures.
- 11. Study participant with known concurrent acute or chronic viral hepatis B or C or human immunodeficiency virus (HIV) infection.
- 12. Study participant has a previously diagnosed psychiatric condition which in the opinion of the investigator may affect self-assessments.
- 13. Study participant with any systemic infection requiring treatment with antibiotics, antivirals, or antifungals within 30 days prior to first dose of the investigational product.
- 14. Male study participants who plan to donate sperm during the study or within 6 months after the last dose. Female patients who plan to donate eggs or undergo in vitro fertilization treatment during the study or within 6 months after the last dose.
- 15. Study participants who are determined by the Investigator to be unsuitable for study enrollment for other reasons

Recruitment of Study participants

This clinical trial has been created to enroll 24 study participants diagnosed with Parkinson's disease. A single site located in Sugar Land; Texas will be used for this clinical trial. Each study participant will undergo a Screening visit, prior to Infusion 1 (Baseline). Each study participant will receive a unique subject identification number which must be entered in the screening log. This screening number will be assigned sequentially in the order in which the study participants are screened. The result of the screening visit should be recorded in the screening log by the study delegated staff. See figure below with Screening log.

A study participant who is screened and does not meet the study entry criteria may be rescreened once only. Investigator discretion should be exercised in determining who may be rescreened. All study participants who are eligible to be re-screened must be fully consented a second time before the second set of screening assessments take place and they will keep their original study participant numbers.

Treatments

HB-adMSCs Infusions

Study subjects must have banked their mesenchymal stem cells with Hope Biosciences to participate in this clinical trial. Study subjects who are randomly assigned during the screening

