A repeat measure mixed model will be used to assess within-subject changes from baseline. correction for multiple comparisons will be employed for post-hoc comparisons. Parkinson's assessment scores (i.e., MDS-UPDRS) at screening and infusion 1 (before treatment) will be averaged and treated as a baseline. Averaging is performed to minimize sources of variance (i.e., patient condition, assessors) and particularly to establish a reliable baseline from which to establish changes.

Data Handling Case Report Forms (CRF)

As used in this protocol, the term CRF should be understood to refer to either a paper form or an electronic data record or both. Reports received by the site, or from the central laboratory should be printed, retained as source documentation and signed by the principal investigator, indicating which values are considered clinically significant and to be reported as AEs if applicable.

Source data is all information, original records of clinical findings, observations, or other activities in a clinical trial necessary for the reconstruction and evaluation of the trial. Source data are contained in source documents

Changes in the Conduct of the Clinical Trial Protocol Amendments

Any change to the protocol will need to have a protocol amendment submitted to the IND, and FDA and IRB must agree prior to proceeding.

Deviations from the Protocol

Deviations from the protocol should not occur. If safety deviations occur, the principal investigator must inform the Monitor, and the implications of the deviations must be reviewed and discussed. Any deviation must be documented in the protocol deviation log. In addition, each deviation must include a description of the deviation, the relevant dates (start and stop), and the action taken. All deviation reports and supporting documents must be kept in the Investigator Site File and in the Trial Master File.

Premature Clinical Trial Termination

Both the Study Investigator and Sponsor have the right to terminate the clinical trial at any time. Should this become necessary, the procedures will be agreed upon after consultation between the two parties. In terminating the clinical trial, the Sponsor and the Study Investigator will ensure that adequate consideration is given to the protection of the best interests of the study participants. Regulatory authorities and IRB will be informed.

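### Protocol and SAP define the baseline of the primary endpoint differently: the mean of screening and pre-dose Infusion 1, or the latest pre-dose score alone

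*SAP*

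**What the plan says.** **Protocol v1.0, Statistical Methods.** For Parkinson's disease scores, "assessment scores (i.e., MDS-UPDRS) at screening and infusion 1 (before treatment) will be averaged and treated as a baseline". The reason follows at once: "Averaging is performed to minimize sources of variance (i.e., patient condition, assessors" are the sources it names.

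**SAP v2.0, section 5.2.** "For all endpoints, the baseline value will be the value obtained at the latest pre-treatment assessment visit". The SAP's worked example takes the same two visits, Visit 1 and Infusion 1, and keeps only the later score. Screening or unscheduled scores serve only when the Week 0 score is missing or was not taken before the dose.

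**Where the baseline is used.** SAP 5.2.1 subtracts it from each post-dose value. SAP 2.3 and 7.1.1 make change in Part II at Week 52 the primary efficacy endpoint. SAP 7.1.4.1 tests it with the Mann-Whitney test.

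**Protocol visit labels.** The Protocol also calls Infusion 1 the baseline visit. Under Investigational Plan it says of Visit 2 that "this visit will be used as a starting point for comparison of" the participant's data, and under Recruitment "Each study participant will undergo a Screening visit, prior to Infusion 1 (Baseline").

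**Schedule.** Table 3 places the Parkinson's disease assessments, including the MDS-UPDRS, at both Visit 1 and Visit 2.

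**The concern.** Both rules cannot be followed. A participant whose screening and Infusion 1 scores differ has two different primary outcomes, depending on which document is used. The SAP does not say that it departs from the Protocol, and the Protocol requires that "Any change to the protocol will need to have a protocol amendment submitted to the IND".

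Two things are at stake. First, two defensible primary results would exist, and the choice between them should not be open once unblinded results are known. SAP 5.5 plans an unblinded interim analysis whose results go to members of the sponsor. Second, the averaging was meant to gain precision. The Mann-Whitney test takes no covariate, so a noisier baseline passes straight into the primary comparison, with at most 12 participants per arm.

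The scope is limited. MDS-UPDRS Parts I–IV and the total score are affected. Laboratory values are not, because the Protocol has its own rule for them: in stated situations, "the laboratory results obtained during Visit 1 Screening will be used as a Baseline". Vital signs and weight are not affected either. PDQ-39, PFS-16, Neuro-QoL and VAS are unclear: the averaging sentence names only the MDS-UPDRS, but the note to Table 3 counts these scales among the Parkinson's disease assessments.

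**Working it through.** There is no figure in the plan to reproduce. The Protocol gives N = 24 (12 per arm) without SD, correlation, effect size or power. The first step below is exact; the rest rests on assumptions and shows scale only.

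**1. Difference per participant.** Let S, I and W be the scores at screening, Infusion 1 and Week 52.

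(W − I) − (W − (S + I)/2) = (S − I)/2

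Illustration: S = 14, I = 10, W = 11 gives 11 − 10 = +1 under the SAP and 11 − 12 = −1 under the Protocol.

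**2. Largest possible gain from averaging.** Assume independent errors with variance s² at each visit, no true change between screening and Week 0, and true-change variance t². The ratio of variances (averaged / single) is (t² + 1.5s²)/(t² + 2s²).

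| t²/s² | 0 | 1 | 3 | 10 |
|---|---|---|---|---|
| ratio | 0.750 | 0.833 | 0.900 | 0.958 |

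The gain is therefore at most 25%.

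**3. A more realistic model.** Assume the true-score correlation decays to r over 52 weeks, measurement error is a share e of the variance, and screening is g weeks before Infusion 1. Then C(d) = (1 − e)·r^(d/52) for d > 0, and in units of the score variance:

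- Single baseline: V = 2 − 2C(52)
- Averaged baseline: V = 1 + (1 + C(g))/2 − C(52) − C(52 + g)

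Middle case r = 0.8, e = 0.10, g = 4: C(4) = 0.885, C(52) = 0.720, C(56) = 0.708. Single: 2 − 1.440 = 0.560. Averaged: 1 + 0.942 − 0.720 − 0.708 = 0.515 (unrounded inputs). The ratio is 0.919.

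With baseline as covariate at Week 52, the residual variances are 1 − C(52)² for the single baseline and 1 − [(C(52) + C(52 + g))/2]²/[(1 + C(g))/2] for the mean. In the middle case the ratio is 0.954.

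| r = 0.6–0.9, g = 1–4 weeks | Unadjusted change | Baseline as covariate |
|---|---|---|
| e = 0.05–0.20 | 0.823–0.975 | 0.882–0.997 |
| 24 / ratio | 29.2–24.6 | 27.2–24.1 |
| e = 0 | 1.001–1.016 | 1.003–1.017 |

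The largest gain is at r = 0.9, e = 0.20, g = 1; the smallest with measurement error is at r = 0.6, e = 0.05, g = 4. Without measurement error averaging is slightly worse, because the screening score is the older one.

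**4. Simulated primary test.** Assumptions: 12 per arm, 20,000 trials per scenario, integer scores 0–52, mean 12, SD 6, r = 0.8 or 0.9, e = 0 to 0.20, g = 4, effect 0, 3 or 5 points, asymptotic Mann-Whitney test at two-sided 0.05 (SAP 2.3).

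- No effect: each rule alone rejects in 4.4–4.7% of trials; the two verdicts differ in 1.6–4.3%.
- Effect of 3 or 5 points, e > 0: averaging adds 1.8 points of power (34.6% to 36.4%; r = 0.8, e = 0.05, 3 points) to 8.8 points (67.3% to 76.1%; r = 0.9, e = 0.20, 5 points).
- Effect of 3 or 5 points, e = 0: averaging changes power by −0.5 to 0.0 points.
- With an effect, over all values of e, the verdicts differ in 0.9–15.5% of trials.

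At the first Holm step of SAP 5.4, 2.5/8% = 0.3125%, the power changes are +0.2 to +6.8 points with measurement error and −1.3 to −0.5 without. That threshold applies only if Part II has the smallest of the eight p-values.

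**The case against.** The SAP is the later document and the statistical one (18 April 2023, against 29 April 2021 for the Protocol). It gives one clear rule with a fallback for a missing score, so an analyst who follows it has no choice to make. Its rule also matches the Protocol's habit of calling Infusion 1 the baseline. The change may be deliberate: a reason in a part of the SAP not available to this review, or in a later protocol version, cannot be excluded. No validity defect follows, since both rules are pre-treatment and treat the arms alike. The preference for averaging rests on an assumed, independent measurement error. The Protocol has the principal investigator evaluate the MDS-UPDRS answers, so a rater effect that is constant over visits cancels from the change under either rule.

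Much of this stands. There is no bias, the size is conditional, and the disagreement rates near 15% come from assumed effects, not from the null case. But the labels only name a visit; the Statistical Methods sentence is the Protocol's only explicit rule for computing the baseline of these scores, and it states its purpose. A later SAP may change that rule, but then it should say so and the Protocol should be amended.

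**Conclusion.** The contradiction is certain and needs no assumption: the two documents give different values of the primary endpoint whenever S and I differ. It threatens neither the comparability of the arms nor the type I error, provided one rule is fixed before results are known. The probable cost of the SAP rule is modest: 2.5–18% of the variance of the unadjusted change if measurement error is 5–20%, and nothing, or a very small gain for the SAP rule, if there is none. It should be fixed, because it concerns the primary endpoint and the correction is cheap.

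For the repeated-measures sensitivity analysis the cost is smaller if baseline is a covariate. The SAP leaves that open: section 5.3.1 includes baseline where applicable, while 7.1.4.1 lists only treatment and visit.

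**What to change.** Amend SAP 5.2 before interim results are released to members of the sponsor or, if that has passed, at the latest before final unblinding:

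- MDS-UPDRS baseline is the mean of the screening and pre-dose Infusion 1 scores.
- If only one of the two exists, use it. Otherwise the participant has no baseline, and SAP 10.1.2.1 allows no imputation.
- For a rescreened participant, use the screening set that led to randomisation. The Protocol allows one rescreening, with the participant "consented a second time before the second set of screening assessments take place", so two screening scores can exist.
- Use an unscheduled pre-dose score only to replace a missing scheduled one.
- State whether the rule covers PDQ-39, PFS-16, Neuro-QoL and VAS. Keep the latest pre-dose value for laboratory tests, vital signs and weight.
- Give the averaged baseline its own label, since SAP 5.2.1 displays baseline with a visit name, and state in SAP 7.1.4.1 whether baseline is a covariate in the repeated-measures model.
- Report the latest-value version as a named sensitivity analysis.

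If the SAP rule is deliberate, amend the Protocol's Statistical Methods section, give the reason, and make the averaged version the sensitivity analysis.

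The cost is one SAP paragraph, one derivation and one table, from scores already scheduled. The alternative route needs a protocol amendment.
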